4.4 LONG-TERM SAFETY SET

Long-term safety set will include safety set who took Esgliteo for 24 weeks or more and include cases followed up at 24 weeks or more after the date of first Esgliteo administration.

4.5 LONG-TERM EFFECTIVENESS SET

Among long-term safety set, the cases below shall be excluded from long-term effectiveness set.

- a. Cases excluded from long-term safety set
- b. Cases with missing information of effectiveness assessment
- c. Cases omitted in final effectiveness evaluation

CONFIDENTIAL

STATISTICAL ANALYSIS PLAN

d. Cases whose final effectiveness evaluation was found to be 'Unassessable'

4.6 SUBJECTS OF SPECIAL INVESTIGATION

Subjects of special investigation include geriatric population (65 years or more), pregnant women, patients with renal impairment, patients with hepatic impairment, long-term use of Esglito (24 weeks or more) among the subjects who conducted investigation for safety assessment after the Esglito administration.

5. GENERAL ANALYSIS CONSIDERATIONS

[figure not shown]
5.1 STATISTICAL ANALYSIS SOFTWARE

Statistical analyses will be performed using a version 9.4 64 bit ([REDACTED] or higher on the SAS® Enterprise Guide (version 8.2 and later) interface.

5.2 GENERAL CONSIDERATIONS

Continuous variables will be summarized with number of subjects, means, standard deviation (SD), median, minimum, maximum, 5th percentile and 95th percentile. Categorical variables will be summarized with frequency and percentage. Unless otherwise specified, statistical tests will be performed at two-sided significance level of 5% for all tests. The mean, median, 5th percentile and 95th percentile present one more significant digit than the original data, and SD presents two more significant digits than the original data. The minimum, maximum values are presented in the same significant digits as the original data, and the percentage, confidence interval, and Odd ratio are presented in two decimal places (rounded from the third position). However, duration of disease, total administration period, and the average number of administrations per day are presented by considering the original data as two decimal places. The p-value is presented to four decimal places (rounded from the fifth digit), <0.0001 if the p-value is less than 0.0001, and >0.9999 if it is greater than 0.9999.

CONFIDENTIAL

STATISTICAL ANALYSIS PLAN

6. DATA HANDLING CONVENTIONS

6.1 HANDLING OF MISSING DATA

All endpoints will be analyzed for OC (observed case) method. In other words, missing data is not replaced.

6.2 HANDLING OF MISSING DATES

If there are missing dates which are needed in calculations, they will be imputed as described in the following.

If date of last safety assessment is missing when processing missing values on end date of administration of Esgliteo, it is replaced with date of last visit.

Table 2 Handling of missing dates

Types of Dates	Missing	Imputation	Examples
Diagnosed date	DD	01	Collected date: 2021-12-UK Imputed date: 2021-12-01
End date of Esgliteo administration	DD	1. [Year-Month] is the same as date of last safety assessment [Year-Month]: date of last safety assessment [Day] 2. [Year-Month] is different from date of last safety assessment [Year-Month]: 31	1. Date of last safety assessment: 2021-12-21 Collected date: 2021-12-UK Imputed date: 2021-12-21 2. Date of last safety assessment: 2021-12-21 Collected date: 2021-11-UK Imputed date: 2021-11-31
Start date of other anti-diabetic agent/	MM-DD	01-01	Collected date: 2021-UK-UK Imputed date: 2021-01-01
Prior/concomitant medications administration	DD	01	Collected date: 2021-12-UK Imputed date: 2021-12-01
End date of other anti-diabetic agent/	MM-DD	12-31	Collected date: 2021-UK-UK Imputed date: 2021-12-31
Prior/concomitant	DD	Last [day] of the month	Collected date: 2021-12-UK

CONFIDENTIAL

STATISTICAL ANALYSIS PLAN

Types of Dates	Missing	Imputation	Examples
medications			Imputed date: 2021-12-31
administration			

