6.3 HANDLING OF DERIVED VARIABLES

The baseline is considered to be the start date of the first administration of Esgliteo and the baseline value is defined as the last value measured before the first administration.

Derivation/imputation of variables will be performed as in the following.

Table 3 Derived variables

Variable	Derivation Method
Change from baseline	Post-baseline value – Baseline value
Age group	Less than 19 years 19 years or older and less than 30 years 30 years or older and less than 40 years 40 years or older and less than 50 years 50 years or older and less than 60 years 60 years or older
Duration of disease (years)	(Date of data release consent – Diagnosed date) / 365.25
Geriatric population	65 years or older, Less than 65 years
Total period of drug use(days)	End date of Esgliteo final administration – Start date of Esgliteo first administration+1 If [Continuing] is checked on CRF [DISPENSING OF ESLITEO] page, end date of Esgliteo final administration will be replaced with date of last safety assessment, and if date of last safety assessment is missing, it is replaced with date of last visit.
10/5mg, 25/5mg Sum of total period of drug use(days)	Sum of ((End date of Esgliteo administration - Start date of Esgliteo administration +1) per duration of visit) If [Continuing] is checked on CRF [DISPENSING OF ESLITEO] page, end date of Esgliteo final administration will be replaced with date of last safety assessment, and if date of last safety assessment is missing,

CONFIDENTIAL

STATISTICAL ANALYSIS PLAN

Variable	Derivation Method
	it is replaced with date of last visit.
Total number of administrations	Sum of (Administration frequency ^[1] ×period of drug use) per duration of visit [1] QD: Once a day, BID: Twice a day, TID: Three times a day, QID: Four times a day, PRN: Whenever necessary But, the value collected with PRN is excluded from analysis.
Average number of administrations per day	Total number of administrations / Total period of drug use
Duration of AE (Days)	AE end date – AE onset date +1 If [Continuing] is checked on CRF [ADVERSE EVENTS] page, AE end date will be replaced with date of last safety assessment, and if date of last safety assessment is missing, it is replaced with date of last visit, and will mark \geq (e.g. ≥ 15).
Onset duration of AE	AE onset date – Date of first Esglito administration
Less than 7% of HbA1c	yes: HbA1c $< 7\%$ no: HbA1c $\geq 7\%$

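### The rule for an Esgliteo end date with a missing day can set day 31 in a month that has none, leaving drug-use duration in those months undefined or dependent on programming

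*SAP*

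**What the plan says.** SAP section 6.2, Table 2, has two branches for an Esgliteo end date whose day is missing.

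- **Branch 1**, recorded month equal to the month of the last safety assessment: "Year-Month] is the same as date of last safety assessment [Year-Month]: date of last safety assessment [Day".
- **Branch 2**, recorded month different: "Year-Month] is different from date of last safety assessment [Year-Month]: 31". The worked example starts from an end date in November 2021 with unknown day and a last safety assessment on 21 December 2021, and gives "Imputed date: 2021-11-31".

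If the last safety assessment date is itself missing, the last visit date stands in for it. For other anti-diabetic agents and prior or concomitant medications with a missing end day, the same table says "Last [day] of the month".

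SAP section 6.3, Table 3, defines total period of drug use as "End date of Esgliteo final administration – Start date of Esgliteo first administration+1". The same end dates enter the period sums for 10/5 mg and 25/5 mg, the total number of administrations and the average number per day. For patients still on drug, "end date of Esgliteo final administration will be replaced with date of last safety assessment", so they do not use the rule above.

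SAP section 4.4 restricts the long-term safety set to patients who "took Esgliteo for 24 weeks or more" and were also followed up at 24 weeks or later. The long-term effectiveness set (4.5) is drawn from it. Protocol section 9.7.5 gives no rule for imputing dates.

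**The concern.** Branch 2 ignores month length, so in some months it produces a date that is not on the calendar. The SAP does not say what happens next. A programmer could let the date become missing, let it roll into the following month, or substitute the last day of the month.

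The variables built on this date are used in several places: the exposure summaries (7.4), the univariate predictors of adverse events and efficacy (8.3.1, 9.4), and the median-split factors for HbA1c change (9.2 item 4, 9.7 item 4). Section 6.1 does not replace missing data, and the multivariable models use complete cases (8.3.2, 9.5). A duration lost to an invalid date would therefore not be recovered. Section 4.4 does not name the derived variable, but the total period of drug use is the natural way to apply its 24-week condition, so long-term-set status may also be affected.

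**Working it through.** **Inputs.** Branches 1 and 2, the example and the rule for other medicines come from SAP 6.2, Table 2. Duration = end − start + 1 comes from SAP 6.3, Table 3. The threshold is 24 × 7 = 168 days (SAP 4.4). The planned data collection runs from 30 Oct 2021 to 30 Nov 2022 (SAP 2.3; protocol section 6).

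**1. The plan's own figure.** November 2021 with unknown day and a December assessment falls under branch 2. Year-month 2021-11 plus day 31 gives 2021-11-31, exactly the SAP's example. The example follows from the rule and is not a slip in the example alone. November has 30 days, so the date is invalid.

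**2. Months in which branch 2 fails.** February, April, June, September and November: 5 of 12. In the other 7, day 31 is the last day and the rule works. October 2021 to November 2022 spans 14 calendar months, of which 6 are short (Nov 2021; Feb, Apr, Jun, Sep and Nov 2022): 6/14 = 43%. A stop in November 2022 reaches branch 2 only if the last assessment fell in another month, which in a window ending 30 Nov 2022 means an earlier one. Without that month the share is 5/13 = 38%. Both are shares of the uses of branch 2, assuming stop months are evenly spread. They are not shares of patients.

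**3. If the date is rejected.** The end date is missing, and so are total period of drug use, the affected period sum, the number of administrations and the average per day.

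**4. If the date rolls over.**
- 30-day month: day 31 becomes the 1st of the next month. For April 2022 this is 1 May against 30 April, so 1 day too long.
- February 2022: day 31 becomes 3 March against 28 February, so 3 days too long.

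**5. Effect on the 168-day condition.**
- *Stops that cannot qualify.* With a start no earlier than 30 Oct 2021, a stop in November 2021 gives at most 2 + 30 = 32 days to 30 November. A stop in February 2022 gives at most 2 + 30 + 31 + 31 + 28 = 122 days, or 125 after roll-over. Day 168 is reached on 15 April 2022 at the earliest. Of the six short months, only April, June, September and November 2022 can matter for set status.
- *Away from the boundary.* Start 1 Nov 2021, end April 2022 with unknown day: 181 days to 30 April, 182 after roll-over. The patient qualifies on duration either way, but is undetermined if the date is rejected.
- *At the boundary.* Start 15 Nov 2021, same end: 16 + 31 + 31 + 28 + 31 + 30 = 167 days to 30 April (below threshold), 168 after roll-over to 1 May (at threshold).
- *How often roll-over changes status.* For each 30-day stop month exactly one start date is affected: 15 Nov 2021 for April, 15 Jan 2022 for June, 17 Apr 2022 for September and 17 Jun 2022 for November. For February 2022 it would be three (15 to 17 Sep 2021), all before the planned start.

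**6. After the change.** With the last day of the month the example becomes 2021-11-30, and every month gives a valid date.

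**The case against.** The case for leaving this alone is that its reach is narrow.

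- Branch 1 takes the day of the last safety assessment, and continuing patients bypass the rule. Branch 2 itself is valid in 7 of 12 months.
- The main outputs do not use this date as defined. Adverse event summaries run on the safety set (SAP 8, 8.1), and HbA1c change runs on visit windows (6.4, 9.1).
- The two rows of Table 2 govern different variables, so the difference between them is an inconsistency of convention and not a direct contradiction.
- Any competent programmer would use the last day of the month.

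The first three points stand and limit the size of the problem. The fourth does not remove it. SAP section 1 requires any departure from the plan, with its reason, to be recorded in the final report, so even the sensible silent repair would be a deviation.

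A reader might also infer more than the documents support:

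- *That long-term-set membership is wrong for these patients.* The SAP does not say how an invalid date is processed, section 4.4 does not name the derived variable, and roll-over changes status only at the boundary.
- *That the loss is not random.* Nothing in the documents shows who has partial end dates.
- *That the lack of a cap at the last safety assessment is part of the error.* Branch 1 already equals that date. In branch 2 a cap matters only if the recorded stop month is later than the assessment month. In the SAP's example it is earlier.

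**Conclusion.** Wrong as written, with probably limited numerical effect. In the five months with fewer than 31 days, branch 2 cannot yield a valid date. The duration variables, and by inference 24-week status, are then either undefined or decided by the program: missing under rejection, or 1 day too long (3 days in February 2022) under roll-over. Rejection is the more damaging case, because it removes the patient from every analysis that needs duration and may leave a patient with 24 weeks or more on drug unclassified. The number of records with a missing end day is not stated, so no effect on any result can be calculated. That the number is small is a judgement. The conclusion that the rule fails rests only on the calendar and the SAP's own text. The month shares assume stop months spread evenly over the planned window.

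**What to change.** In SAP Table 2, change branch 2 so that the missing day becomes the last calendar day of the recorded month, as the table already does for other medicines. Correct the example to 2021-11-30. This costs one line and its example. In the seven 31-day months the imputed date does not change, so there is no analytic downside. As an optional extra, add that the imputed date may not be later than the last safety assessment, or the last visit if that is missing. This would cover a recorded stop month that falls after the last assessment.

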9.2.3.2 Visit 1; Baseline Visit

Upon patient enrolment, the following will be recorded on the patient's eCRF.

- Visit date
- Diagnosis: date of the diagnosis of T2DM, Family history of T2DM
- Inclusion / Exclusion criteria
- Data release consent form: Date of data release consent form

Boehringer-Ingelheim**Non-interventional Study Protocol****BI Study Number 1275-0028****c37168579-01**

Proprietary confidential information © 2022 Boehringer Ingelheim International GmbH or one or more of its affiliated companies

- Demographic data: Year of birth(age), Gender, Pregnancy, Previous allergy, Height, Smoking status
- Diabetes mellitus related complication(Retinopathy, Neuropathy, Nephropathy, Vasculopathy, Others)
- Medical history: Renal impairment, Hepatic impairment, Others. (history of concomitant disease within 6 months prior to baseline)
- Physical examination: Body weight, Blood pressure (SBP, DBP)
- Renal function test: Serum creatinine, eGFR, Urine ACR if blood test result is available(the most recent data prior to baseline)
- Effectiveness assessment: HbA1c, FPG (within 1 month prior to baseline)
- Concomitant anti-hyperglycemic agent: record any anti-hyperglycemic agents that have been taken at least once (within 1 month prior to baseline)
- Concomitant medications: record all medications that have been taken at least once (within 1 month prior to baseline)
- Dose of Esgliteo given (Daily dose, Start date)

At visit 1, the patient will be requested to contact the treating physician in the event of any adverse events noted after initiating Esgliteo treatment.

9.2.3.3 Visit 2; 12 weeks from Visit 1

After 12 weeks from Visit 1, the patients will return for follow-up. The followings will be noted and recorded in the eCRF.

- Visit date
- Physical examination: Body weight, Blood pressure (SBP, DBP)
- Any changes of Esgliteo given
- Effectiveness assessment: HbA1c, FPG (Within 1month prior to Visit 2)
- Renal function test: Serum creatinine, eGFR, Urine ACR if blood test result is available (The most recent data since last visit, except previously entered data)
- Concomitant anti-hyperglycemic agent including new medications taken since last visit: any changes in the concomitant medications (dose and dosing intervals)
- Concomitant medications including new medications taken since last visit: any changes in the concomitant medications (dose and dosing intervals)

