7.3.5 Prior and concomitant medication

Prior medication is defined as any medication that the subjects took before the first dose of Esgliteo. Concomitant medication is defined as any medication that the subjects took on or after the first dose of Esgliteo.

Prior medication is any medication that can be classified into the following category.

- Medication start date < Start date of first Esgliteo administration

Concomitant medication is any medication that can be classified into the following category.

- Medication start date \geq Start date of first Esgliteo administration

Table 5 Examples of categorization

Medication start date	Medication end date	Date of first Esgliteo administration	Prior medication	Concomitant medication
2020-01-01	2020-01-14	2020-01-15	Y	
2020-01-01	2020-01-15	2020-01-15	Y	
2020-01-01	2020-01-20	2020-01-15	Y	
2020-01-01	Ongoing	2020-01-15	Y	
2020-01-15	2020-01-15	2020-01-15		Y
2020-01-15	2020-01-20	2020-01-15		Y
2020-01-15	Ongoing	2020-01-15		Y
2020-01-20	2020-01-25	2020-01-15		Y
2020-01-20	Ongoing	2020-01-15		Y

If there is a missing date, Prior/concomitant medication is classified by processing according to [6.2 Handling of Missing Dates].

Prior and concomitant medications will be summarized with number of subjects, percentages and number of cases. Prior and concomitant medications will be coded using the World Health Organization Anatomical Therapeutic Chemical index (WHO ATC index) latest version and

CONFIDENTIAL

STATISTICAL ANALYSIS PLAN

will be summarized with Level 1 (anatomical main group) and Level 5 (chemical substance) using number of subjects, percentages and number of cases. However, if level 5 is 'Combinations', 'Various' or 'various combinations', then level 4 will be used instead. (If level 5 doesn't exist then a higher level will be used.) The frequency is counted as one person in each classification (Subjects investigated with prior and concomitant medication, level 1 and level 5) even if one subject has multiple prior/concomitant medications.

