8.3 SAFETY ANALYSES BY FACTORS

8.3.1 Univariate analysis

The following categorical variables will be summarized using number of subjects, the number of subjects and proportion of the number of subjects with AE and 95% confidence interval. AE Occurrence will be analyzed using Pearson's chi-square test or Fisher's exact test to determine if statistically significant differences exist. (However, if [Diabetes mellitus complications] responds with [Not applicable], [Pregnancy] responds with [Not applicable], [Height] responds with [Not done], it is excluded from Pearson's chi-square test or Fisher's exact test.)

- Gender (Male, Female)
- Smoking status (Never smoked, Ex-smoked, Currently smokes)
- Family history of T2DM (Yes, No)
- Previous allergy (Yes, No)
- Diabetes mellitus complications (Retinopathy, Neuropathy, Nephropathy, Vasculopathy, Other) (Yes, No, Not applicable)
- Medical history (Yes, No)
- Comorbidities (Yes, No)
- Prior medication (Yes, No)
- Concomitant medication (Yes, No)
- Other anti-diabetic agent (Yes, No)

For the following continuous variables AE Occurrence will be summarized using odds ratio and 95% confidence interval for an increase or decrease per defined unit of the variable based on using simple logistic regression.

- Age (years)
- Height (cm)
- Weight (kg)

CONFIDENTIAL

STATISTICAL ANALYSIS PLAN

- Duration of disease (years)
- Total period of drug use (days)
- Total number of administrations
- Average number of administration per day

Subjects of special investigation will be summarized using number of subjects, number of subjects with AE, proportion of subjects with AE and 95% confidence interval. AE Occurrence will be analyzed by using Pearson's chi-square test or Fisher's exact test to confirm statistically significant differences.

- Geriatric population (65 years or more, Less than 65 years)
- Pregnant women (Yes, No, Not applicable)
- Renal impairment (Yes, No)
- Hepatic impairment (Yes, No)
- Long term use (24 weeks or more)

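### Partial medication start dates are imputed without regard to the first Esgliteo dose, so a drug first recorded at Visit 2 or 3 can be counted as Prior medication

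*SAP*

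**What the plan says.** SAP 6.2, Table 2, has one row for start dates of other anti-diabetic agents and of prior or concomitant medications. With the day missing, the date becomes the first of the month: "Collected date: 2021-12-UK Imputed date: 2021-12-01". With month and day missing, it becomes 1 January: "Collected date: 2021-UK-UK Imputed date: 2021-01-01". Neither rule refers to the first Esgliteo date. By contrast, the row for the end date of Esgliteo in the same table uses a reference date, the last safety assessment.

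SAP 7.3.5 calls a drug Prior when "Medication start date < Start date of first Esgliteo administration", and Concomitant otherwise. The end date plays no part, and Table 5 marks each drug as one or the other, never both. The section carries the imputation straight into the classification: "If there is a missing date, Prior/concomitant medication is classified by processing according to [6.2 Handling of Missing Dates". No exception is given.

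Protocol 9.2.3.3 and 9.2.3.4 have the site record at Visits 2 and 3 "Concomitant medications including new medications taken since last visit", in an entry that also covers changes of dose and dosing interval. Protocol 9.2.3.2 has the site record at Visit 1 every medication taken in the month before baseline.

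**The concern.** A drug that the site reports at Visit 2 or 3 as new since the last visit was, on the site's own report, not being taken before treatment began. If its start date is incomplete, Table 2 can still place it before the first dose, and the SAP then counts it as Prior. The rule overrides information that the study collects.

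The shift goes one way: starts are moved earlier, never later. Table B6 (prior medication) can gain drugs begun on treatment, and so can the Yes/No factor Prior medication in SAP 8.3.1, 9.2(4), 9.4 and 9.7(4). A drug given to treat an adverse event could then appear as a pre-treatment characteristic associated with that event.

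**Working it through.** **Inputs.** The imputation rules come from SAP Table 2 and the classification from SAP 7.3.5. The dates for start and end of data collection, 30 Oct 2021 and 30 Nov 2022, come from SAP Table 1. The 168-day follow-up is the 24 weeks of Protocol 9.2.3.4.

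**Step 1: reproduce the plan's examples.** With first dose 2020-01-15, the 7.3.5 rule gives Prior for Table 5 rows 1 to 4 and Concomitant for rows 5 to 9, as printed. Both Table 2 start-date examples also reproduce.

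**Step 2: hide part of the date.** Keep the first dose at 2020-01-15.

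| True start | Recorded as | Imputed | Class |
|---|---|---|---|
| 2020-01-20 | complete | none needed | Concomitant (as in Table 5) |
| 2020-01-20 | 2020-01-UK | 2020-01-01 | Prior (wrong) |
| 2020-02-10 | 2020-02-UK | 2020-02-01 | Concomitant |
| 2020-02-10 | 2020-UK-UK | 2020-01-01 | Prior (wrong) |
| any day in 2021 | 2021-UK-UK | 2021-01-01 | Concomitant |

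The error therefore needs the known part of the date to match the month (day missing) or the year (month and day missing) of the first dose. It does not occur if the first dose was on the 1st of the month or on 1 January respectively. With visits on schedule, a drug new since Visit 2 cannot share the first-dose month, so at Visit 3 only year-only dates are affected.

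**Step 3: size within the first-dose month.** Take a 30-day month with uniform dose and start days. Pairs with the start on or after the dose number 30 + 29 + ... + 1 = 465 of 900. Dose on day 1 (30 pairs) is classified correctly. That leaves 435, and 435/465 = 0.935.

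**Step 4: size over the whole follow-up.** Assumption: first doses are spread evenly from 30 Oct 2021 to 15 Jun 2022 (168 days before 30 Nov 2022), and true starts evenly over the 168 days from the first dose. That is 63 dose days in 2021, 1 January 2022, and 165 further days, so 229 × 168 = 38,472 combinations.

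- Day missing: combinations turned Prior, by dose month from October to June, are 3 + 435 + 465 + 465 + 378 + 465 + 435 + 465 + 315 = 3,426. The share is 3,426/38,472 = 0.089, ranging from 0 to 30/168 = 0.179 by dose date. Doses on the 1st add 242 same-month combinations classified correctly, so within the matching month the share is 3,426/3,668 = 0.934.
- Month and day missing: dose days in 2021 give 63 + 62 + ... + 1 = 2,016. Dose on 1 January gives 0. The other 165 dose days give 165 × 168 = 27,720, because every start then falls in 2022. The share is 29,736/38,472 = 0.773, ranging from 0 to 1 by dose date.

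**Step 5: from records to subjects.** Prior medication is one Yes/No value per subject. It turns from No to Yes only if the misdated drug is the subject's only prior drug on record. Table B6 is affected record by record.

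**The case against.** The strongest case for leaving Table 2 alone is that its rule is usually right for drugs recorded at Visit 1. Take the 2021-UK-UK example with a first dose between 30 Oct and 31 Dec 2021. If starts are spread evenly over 2021, 302/365 to 364/365 of them (83% to 99.7%) truly precede the dose. The common repair, moving every ambiguous start to the first-dose date, would make all of the ongoing ones Concomitant. In the first-dose month it would exchange a 435/900 = 48% error for one of the same size in the other direction, since 435 of the 900 pairs have the start before the dose. That stands, and it rules out a blanket change.

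Three further limits also stand.

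- The loss of these drugs from Table B7 is not due to Table 2 alone. SAP 7.3.5 says in words that "Concomitant medication is defined as any medication that the subjects took on or after the first dose of Esgliteo", but its working rule looks only at the start date. If the worded definition were applied, a misdated drug still in use after the first dose would return to Table B7. Its surplus entry in Table B6 would remain, and that part belongs to Table 2.
- Other anti-diabetic agents share the Table 2 row, but SAP 7.3.6 summarises them by use during the study and they have their own factor. A reader might infer that drugs added for poor glycaemic control are relabelled as Prior; the text does not establish that.
- Protocol 9.10.2.1 expects concomitant therapy start dates from source documents, so partial dates may be few.

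**Conclusion.** The rule as written allows a classification that the study's own visit records contradict, and neither document adds a safeguard. The point is minor.

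The shares in the working are conditional on a post-dose start having a partial date, and on even spreads of doses and starts that the documents do not give. The number of partial dates is unknown, so the effect on Table B6 and on the tests of the Prior medication factor cannot be sized.

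A reader might infer that every partial start date becomes Prior wrongly. The documents do not support this: later-month dates with the day missing and later-year dates with month and day missing are classified correctly, and for drugs recorded at Visit 1 the present rule is often right. Nor do they support an inference that the overall adverse event incidence or the mean HbA1c change is biased, because neither uses this classification.

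**What to change.** Add one rule to SAP Table 2. For a medication first recorded at Visit 2 or 3 as new since the last visit, impute the start as the later of (a) the date under the present rule and (b) the day after the subject's preceding visit. The result must stay within the known month or year and not pass the recorded end date. Keep the present rule for medications recorded at Visit 1 as taken before baseline.

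The cost is a line in Table 2 and a small program change. The program needs the visit at which each drug was first recorded, and entries that only report a change of dose or interval must be separated from new drugs. The case report form is not among the documents, so whether it holds a flag for this must be checked. If the first dose was taken some days after Visit 1, a drug started in between stays ambiguous, and the SAP should say how it is classed. SAP 1 already provides for recording a changed method and its reason in the final report.
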